7.0 Expected Risks/Benefits

There will be no direct benefit to participants for participation in this study, other than they will be compensated for their time for participation in this study. The study will be used to further our knowledge on the potential utility of suvorexant for the treatment of AUD.

Diagnostic/Assessment Procedures: The diagnostic interview and questionnaires are time consuming and may be boring to some individuals. These are, however, necessary in order to determine eligibility for the study and test hypotheses. In addition, questions about alcohol/drug use, abuse/trauma history, and questions related to history of suicidal and/or homicidal behavior may be considered sensitive by some participants. The collection of such data poses a potential risk of loss of confidentiality around sensitive information such as psychiatric status and history of substance abuse. Participants will also be informed in the consent document that confidentiality will be limited in cases where the participant reveals intentions to harm themselves or others, and the investigator feels that the proper authorities may need to be notified in order to prevent the occurrence of harm to the participant, or others. Interviews will be conducted by experienced mental health workers who will maintain confidentiality and all data from interviews and questionnaires will be numbered so as to conceal the identity of the participant.

Tasks: Some subjects may feel anxiety in response to the acoustic startle probes during the startle task. The experience of mild, electrical stimulation during the threat task elicits temporary mild anxiety by design. Any distress experienced while participating in the study is unlikely to persist beyond completion of study procedures. It should be noted that neither the acoustic startle probes nor the electrical stimulation to be used in the study present greater than minimal risk. The startle probe is a 40ms, 103dB burst of white noise – 10,000 times lower than Occupational Safety and Health Administration guidelines for maximum daily acoustic energy exposure for adults. Moreover, studies have used more intense acoustic stimuli with infants with no adverse effects. The electrical stimulation lasts only 400ms, and the maximum stimulation level is 5 mA. This is in the ampere range used by physical therapists and chiropractors, but of a much shorter duration. This level of stimulation presents no risk of physical injury. The PI and/or Co-I will be available during all tasks in order to evaluate and recommend treatment for the emergence of any anxiety/panic attack or elevated levels of anxiety.

Magnetic Resonance Imaging: Magnetic resonance imaging is non-invasive, widely used, and safe. The potential risks such as static magnetic field, radio-frequency field, magnetic field gradients, and acoustic noise are rarely dangerous or life threatening. Additional minor and/or rare risks include: (a) discomfort or anxiety from being in the confined space of the MRI scanner; (b) fast imaging sequences, such as those employed

in this study, have the potential to induce peripheral nerve stimulation (PNS). PNS can be described as a light touching sensation on the skin surface and may cause mild discomfort, but is not harmful to the subject; (c) risks of hearing damage due to loud noises produced by the scanner; (d) risk that the magnetic resonance image will reveal a minor or significant lesion in the brain, e. g. a tumor, previously unknown to the subject, and requiring additional follow-up; (e) risk of injury from objects accelerated by the strong magnetic field of the magnet, striking the subject; or metallic substances on the skin or foreign bodies implanted deliberately or accidentally in the subject that acquire kinetic or thermal energy from the magnetic or radiofrequency emissions of the MRI, causing tissue injury to the subject; (f) sometimes, subjects report a temporary, slight dizziness or light-headedness when they come out of the scanner; (g) potential risk for pregnant women: According to the NIMH Council Workgroup on MRI Research and Practices (September, 2005), “there is no known risk of MR brain scanning of a pregnant woman to the developing fetus for scanning at 4T or less, and no known mechanism of potential risks under normal operating procedures.” Nevertheless, subjects should be warned about potential risks not yet discovered.

Discovery and disclosure of incidental finding or abnormality on MRI scans: During the formal consent process, all subjects will be informed about the potential risks of discovering an incidental finding or abnormality on their MRI scan. The Center for Cognitive and Behavioral Brain Imaging is a research center. It is NOT a Clinical MRI facility in a hospital. There are no neuroradiologists at the Center for Cognitive and Behavioral Brain Imaging, therefore the staff are unable to make any medical comments on the scans. However, all structural scans obtained in normal research subjects are sent to a neuroradiologist for review. In addition, participants are given the structural images on a CD. In the event the neuroradiologist detects an abnormality, the Center staff will forward his findings to the participant primary care physician (PCP) within one month of the scan. The participant and PCP will receive information that the neuroradiologist has found some abnormalities that could be potentially significant. This will be communicated by a letter. The neuroradiologist will be available to consult with the PCP if it is necessary. Any costs associated with seeing the primary care physician will be participant responsibility. If participants cannot designate a primary care physician in the MRI Screening Form, they cannot participate in the study. Normal scan results will be available one month after the study and will not be communicated to a primary care physician.

Suvorexant-Related Risks: Suvorexant is a Drug Enforcement Administration (DEA) schedule IV-controlled substance in the United States because it is considered to have abuse liability similar to other approved sleep medications (e.g., zolpidem). Preclinical self-administration studies in rats and monkeys indicate suvorexant does not have positive reinforcing effects⁶⁵. In previous clinical trials there has been no evidence of physical dependence with the prolonged use⁶⁶. There is also no evidence of withdrawal or “discontinuation syndrome” following abrupt discontinuation⁶⁶.

Suvorexant is associated with some potential adverse side-effects including: sleepiness or drowsiness, headache, nausea, dizziness, diarrhea, dry mouth, and abnormal dreams. Next day drowsiness is considered the most common side-effect. All

other side-effects have an incidence between 1-10%. Rare but potentially serious side effects include: worsening of depression and increase of suicidal ideation, complex sleep behavior and sleep paralysis, and temporary weakness in legs. Taking a CNS depressant (e.g., benzodiazepines, opioids, some antidepressants and anxiolytics, other sleeping medication) increase the risk of side effects and should not be taken at the same time as suvorexant. Suvorexant should not be taken with grapefruit juice, as this may significantly increase the levels of medication in the blood. Suvorexant should not be taken unless individuals are able to stay in bed for a full night (at least 7 hours) before they must be active again. Individuals should also not drive, operate heavy machinery, or do other activities that require clear thinking immediately after taking suvorexant.

Co-I, [name], M.D., is a Board-certified psychiatrist and physician, and will be available during the Acute Drug Challenge and Drug Trial in order to evaluate and/or recommend further evaluation and treatment for the emergence of any adverse events/side effects. Participants taking psychoactive/psychotropic medications or medications that would interact with suvorexant will be excluded. Pregnant participants will be excluded from participation because there is insufficient data to assure safety of the fetus during suvorexant exposure. As well, female participants who are not using acceptable methods of contraceptives or abstinence will be excluded. In addition, nursing mothers will be excluded from the study because the extent to which suvorexant is concentrated and excreted in human breast milk is unknown. Participants will be fully debriefed following the study. During debriefing, any questions participants may have will be answered.

Drug-Alcohol Interactions: To date, there have been at least three human laboratory studies that have directly investigated the pharmacokinetic (PK) and pharmacodynamic (PD) interactions between ethanol and orexin antagonists⁶⁷⁻⁶⁹. All three studies used the highest possible dose of orexin-based medication to robustly probe for the potential for ethanol interactions (e.g., 40mg of suvorexant). All three studies confirmed that coadministration with ethanol does not alter the PK of orexin therapeutics, apart from potentially prolonging time to reach maximum plasma concentration (t_{max}) by about 75 mins. There is no effect of orexin therapeutics on the ethanol concentration versus time profile. With regard to PD, co-administration produced additive impairment on measures of sustained attention/vigilance, balance, and working memory. There was no evidence of supra-additive effects. High doses of orexin antagonism alone, and in combination with ethanol, were well tolerated with no severe or serious AEs reported and no observed effects on clinical laboratory or cardiac variables. Mild to moderate treatment emergent adverse events (TEAEs) reported following co-administration included headache, fatigue, and sudden onset of sleep. There was no impact of co-administration on positive or negative mood. All three studies concluded that concomitant use of alcohol and orexin-based antagonists should be avoided due to the potential for additive psychomotor effects; though there are no serious concerns regarding safety and tolerability like with other sleep medications such as hypnotics. Participants will be informed of these risks during informed consent and at the Acute Drug Challenge Visit.

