4.2 Exclusion Criteria

Exclusion criteria for all subjects will be: (a) clinically significant medical or neurologic condition or neurocognitive dysfunction that would affect function, and/or task performance, and/or interfere with the study protocol, and/or be contraindicated for suvorexant (SUV), including narcolepsy, complex sleep behaviors, severe hepatic impairment, and compromised respiratory function such as COPD, and severe obstructive sleep apnea; (b) current or past major DSM-5 psychiatric disorder including mania, schizophrenia, psychosis, suicidality (as defined by a score of 5 or higher on the Beck's Scale for Suicidal Ideation - Lifetime [SSI]), major depressive disorder (MDD), or obsessive-compulsive disorder (OCD); (c) current substance use disorder for any substance, except for mild cannabis use disorder; (d) treatment seeking for AUD due to the study design and experimental nature of SUV; (e) currently pregnant (positive pregnancy test), lactating, or not agreeing to use birth control methods during the duration of the trial (women); (f) recent (in the past 2 months) use of any psychoactive medications; (g) current antihistamines use; (h) current use of strong or moderate inhibitors of CYP3A liver enzymes; (i) current use of strong CYP3A inducers; (j) current use of digoxin; (k) night shift work; (l) smoke 5 or more cigarettes (or electronic equivalent) per day and are thus susceptible to acute nicotine withdrawal during lab visits; (m) obesity as defined by a body-mass index (BMI) greater than 35, as calculated from weight and height self-report; (n) lack of fluency in English; (o) acute alcohol withdrawal the day of the lab sessions, defined as a score >8 on the Clinical Institute Withdrawal Assessment of Alcohol Scale Revised (CIWA-Ar)²⁹; (p) unwilling/unable to sign the informed consent document; (q) under 18 years old or over 65 years old at the time of enrollment; (r) history of traumatic brain injury (as defined by The American Congress of Rehabilitation as a traumatically induced physiological disruption of brain function - i.e., the head being struck, the head striking an object, and/or the brain undergoing an acceleration/deceleration movement, such as whiplash - without direct external trauma to the head), as manifested by at least one of the following: any loss of consciousness; any loss of memory for events immediately before or after the injury; any alteration in mental status at the time of the incident; or focal neurological deficits that may or may not be transient.

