- Following the Screening Session, eligible participants will be randomized to a treatment group (i.e., SUV or placebo) and protocol arm (i.e., EMG/EEG only or EMG/EEG + fMRI). Treatment group randomization will be double-blinded.
- Research study staff will monitor the participants throughout the course of the research to ensure that they still meet eligibility criteria, and their continuing eligibility will be documented by the research staff. This will include ensuring abstinence from alcohol at both laboratory visits. It will also ensure that no participant is pregnant at either session.
- Upon enrollment into the study, participants will be required to agree and consent to not operating heavy machinery, including driving a vehicle, for at least 24-hours after the Acute Drug Challenge visit due to day-time drug administration.
- Participants will also be instructed that they will be required to fast for at least 2-hours prior to the Acute Drug Challenge visit to avoid interactions between food and SUV metabolism. The Acute Drug Challenge visit will therefore begin at approximately 9-10am.
- Following the Acute Drug Challenge visit, participants will be instructed to take either SUV or placebo, dependent upon their randomized treatment group, once daily before bed for 4 weeks. Participants will complete daily online clinical assessments. The PI and study staff will monitor potential side effects and drug adherence throughout the duration of the 4 weeks.
- Participants will return to the lab at the end of the 4 weeks and complete a third EMG/EEG, and second fMRI (dependent upon randomization).
- Participants will be debriefed and provided AUD treatment referrals as appropriate at the end of their study participation.

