Study Overview. The study is a double-blind, between-subjects, randomized clinical trial with a multi-session lab paradigm (see Figure 1). Participants will first complete an initial Screening Session where they will complete an assessment of study eligibility (described above), a clinical interview, and questionnaires. If participants are found to be eligible, they will be randomized to a treatment group (SUV or placebo) and protocol arm (BEHAVIOR or BRAINS Group). Those in the BEHAVIOR Group will complete electromyography (EMG)/electroencephalography (EEG) only and those in the BRAINS Group will complete EMG/EEG + fMRI.

Therefore, participants have a chance of being randomized to four different groups (20 participants/group): 1) BEHAVIOR - SUV; 2) BEHAVIOR - Placebo; 3) BRAINS - SUV; and 4) BRAINS - Placebo.

BEHAVIOR Group Overview:

Following the Screening Session, participants randomized to the BEHAVIOR group will come in-person to Lab Visit 1 where they will complete the psychophysiological stress paradigm and Alcohol Cue Reactivity EEG task. Days later, they will return to the lab for Visit 2 (Acute Drug Challenge) and repeat the protocol during their first dose of medication (placebo or 10mg SUV). Next, they will be instructed to take a 10mg dose of SUV (or placebo) each night before bed for 4-weeks. Daily online assessments of medication compliance, side-effects, alcohol use, mood, and sleep will be collected. During the final week of the protocol subjects will return for Lab Visit 3 to repeat the paradigm (dose taken night prior, as prescribed).

BRAINS Group Overview:

Following the Screening Session, participants randomized to BRAINS Group will complete the same procedures as above with the exception of completing two additional fMRI visits pre- and post-treatment. Therefore, participants will complete: Lab Visit 1 (EMG/EEG), Lab Visit 2 (fMRI), Lab Visit 3 (Acute Drug Challenge), four weeks of SUV (or placebo) administration with daily online assessments, Lab Visit 4 (EMG/EEG), and Lab Visit 5 (fMRI).

Screening. During the Screening Session, participants will complete an assessment of study eligibility, the Structured Clinical Interview for DSM-5 (SCID-5)³¹ with trained study staff, and a short battery of self-report questionnaires (see Table 1 and Table 2). Participants will be given the choice to complete the Screening Session online or in-person to accommodate potential limited access to the internet.

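### In the BRAINS group, no step sends an abnormal pre-treatment brain scan read to the study physician or PI, and the one-month limit for forwarding it can run through much of the dosing period

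*Combined protocol and SAP*

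**What the plan says.** The paragraph on incidental MRI findings in section 7.0 explains that the imaging center is not a clinical facility: "therefore the staff are unable to make any medical comments on the scans". Structural scans therefore go to a neuroradiologist. For an abnormal scan, "the Center staff will forward his findings to the participant primary care physician (PCP) within one month of the scan". It continues: "The participant and PCP will receive information that the neuroradiologist has found some abnormalities that could be potentially significant", by letter, and the neuroradiologist may be consulted by the primary care physician (PCP). The paragraph names no one on the study team as a recipient. It describes the scans to be reviewed as those of normal research subjects.

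Four other places bear on this:

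- Section 4.2, exclusion (a), covers a "clinically significant medical or neurologic condition or neurocognitive dysfunction that would affect function, and/or task performance", or one that interferes with the protocol or is a contraindication to suvorexant.
- Section 5.0 states: "Research study staff will monitor the participants throughout the course of the research to ensure that they still meet eligibility criteria". Its termination criterion (d) includes a neurologic illness that needs treatment and would exclude participation.
- Section 5.0 also describes the neurologic check at screening, which is a physician's review of history. Randomization follows screening.
- Section 6.0 gives the BRAINS order: "Lab Visit 1 (EMG/EEG), Lab Visit 2 (fMRI), Lab Visit 3 (Acute Drug Challenge), four weeks of SUV (or placebo) administration".

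**The concern.** The plan gives the study team a continuing duty on neurologic eligibility and obtains a test that can bear on it, but has no step that brings the result to that team. A history review cannot show a lesion the participant does not know about, and the MRI risk list in section 7.0 foresees exactly such a finding. Other safety information is routed explicitly. Under section 6.0 the study physician reviews the health questionnaire and medication history before randomization, and reported side effects and new medications during the trial. The scan read has no such route.

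The timing adds to this. The scan comes before the first capsule, but the forwarding limit is about as long as the dosing period. Followed as written, the plan allows a participant with a flagged scan to take a large part of the course before the letter is sent, and then relies on the participant or PCP to tell the study.

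**Working it through.** The plan states no figure on this point, so there is none to reproduce. The check has two parts.

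**1. Who receives the read.**

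- Section 7.0 (incidental findings): PCP and participant.
- Section 6.0 (Drug Trial and Monitoring): the listed daily survey items do not include new diagnoses or scan results.
- Section 11.0: the weekly staff review covers accrual, consent, adherence, adverse events and data quality. Scan reads are not listed.
- Sections 4.2 and 5.0: duties on eligibility and termination, without a source for the scan result.

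No section closes the loop. The text is silent; it does not forbid telling the study team.

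**2. How much dosing can precede the letter.**

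Inputs from the documents:

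- Forwarding limit: one month after the scan, taken as day L = 28, 30 or 31, with the scan on day 0.
- Nightly dosing: 4 weeks × 7 = 28 doses after the acute dose.
- BRAINS group: 20 + 20 = 40 of 80, with 20 on suvorexant.

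Assumed inputs:

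- Scan-to-acute-dose gap, g days. The documents give none for BRAINS. For the BEHAVIOR group, section 6.0 says of the interval after the first lab visit: "Days later, they will return to the lab for Visit 2 (Acute Drug Challenge". I show 1 to 14 days.
- First nightly dose on the day of the acute dose (s = 0) or the day after (s = 1).

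Nightly doses taken before day L = the smaller of 28 and L − g − s. For g = 7 and L = 30, this is 30 − 7 − 0 = 23 or 30 − 7 − 1 = 22. Each range below covers s = 1 to s = 0.

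| Gap g (days) | Letter day 28 | Letter day 30 | Letter day 31 |
|---|---|---|---|
| 1 | 26–27 | 28 | 28 |
| 2 | 25–26 | 27–28 | 28 |
| 3 | 24–25 | 26–27 | 27–28 |
| 7 | 20–21 | 22–23 | 23–24 |
| 14 | 13–14 | 15–16 | 16–17 |

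For a letter on day 30 or 31, that gives 15–17 of 28 doses with a 14-day gap and 22–24 with a 7-day gap. All 28 are taken only when the gap is about 1 to 3 days. The acute dose precedes the letter in every cell. A letter sent well before the limit lowers every count.

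**Number of people.** The documents give no rate of abnormal reads. Purely as an assumption, 1–3% clinically relevant findings would mean 40 × 0.01 to 40 × 0.03 = 0.4 to 1.2 scanned participants, of whom 20 × 0.01 to 20 × 0.03 = 0.2 to 0.6 would be on suvorexant. Fewer would meet exclusion (a).

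**The case against.** The strongest reply is that the scan was never meant as an eligibility screen. Neurologic eligibility is judged from history before randomization, and the 40 BEHAVIOR participants take the same capsules with no scan. On this view the paragraph is a disclosure notice from a non-clinical imaging center, and it contradicts nothing in sections 4.2 or 5.0. That is fair as to intent. But once a read exists, the continuing duty in section 5.0 applies to what it shows, and the plan does not connect the two.

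Several limits stand in full:

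- A reader might infer that the study team can never learn of the finding. The documents do not support that. The participant receives the letter and a CD of the structural images, completes daily surveys, and is under continuing eligibility monitoring. Any of these could bring the finding out; none is a step designed to do so.
- A reader might infer that dosing will be over before anyone knows. One month is a maximum, and the neuroradiologist and center staff know before the letter goes. Longer gaps also fit the plan. Section 3.0 gives 1.5 to 2 months overall, so with 30-day months, 45 − 28 = 17 to 60 − 28 = 32 days lie outside nightly dosing.
- An abnormality is not automatically exclusionary. Criterion (a) is qualified, and section 7.0 speaks only of possible significance.
- A reader might infer damage to the fMRI results. The treatment analysis of the imaging data is labelled exploratory, section 6.0 includes quality checks on motion and normalization, and no effect on a result has been shown.

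The reference to normal research subjects may be generic center wording, since the same paragraph says all subjects are informed about incidental findings. That makes it a clarification, though a useful one where every participant has moderate to severe AUD.

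**Conclusion.** The concern holds as a gap in routing and timing. An abnormal structural read is assigned to the participant and PCP, may be forwarded as late as one month after the scan, and is not sent to those who judge continuing eligibility.

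It applies to 40 of 80 participants, 20 of them on suvorexant. With a letter on day 30 or 31 and assumed gaps of 7 to 14 days, 15 to 24 of 28 nightly doses precede it. The whole course precedes it only in the corner case of a gap of about 1 to 3 days and a letter at the limit. These counts rest on an unstated gap.

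The number of participants concerned is unknown and probably small, and only some findings would meet exclusion (a) or termination criterion (d). No bias in any analysis is claimed. The point merits a change because the possible consequence is a safety matter and the remedy is cheap.

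**What to change.** In the incidental-findings paragraph of section 7.0:

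- name the study physician as a recipient of any abnormal read, at the same time as the PCP;
- replace the reference to normal research subjects with all study participants.

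Then reconcile that paragraph with exclusion (a) in section 4.2, the monitoring duty and termination criterion (d) in section 5.0, and the BRAINS visit order in section 6.0, so that the plan states how the pre-treatment read relates in time to first dosing. Which rule to adopt is for the sponsor and investigator.

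The cost is one more recipient on an existing report, a sentence in the consent form, and a recorded physician review of each flagged scan. Section 13.2 would also need updating, because it says that the only protected health information collected is name and contact details. No new scan or reader is needed. If the timing rule links first dosing to the read, some first doses could be delayed; the sponsor should weigh that when setting it.
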